## Protocol

### 1. Abstract

Family caregivers who care for older adults living with multiple chronic conditions, including heart failure (HF), provide substantial cost savings to the US healthcare system. While caregiving can be meaningful and rewarding, extensive research also demonstrates high rates of chronic disease, fatigue and physiologic measures such as stress hormones among caregivers. Family caregivers are often left juggling their loved one's healthcare as well as their own. Unmet needs have been identified including increased stress, financial strain and social isolation, but interventions to address these needs in HF caregivers have had mixed results. Due to the limited impact of many caregiver interventions, experts have called for a greater understanding of the dynamic and contextual factors of family caregiving including resources, needs and social support with an increased focus on individualization of interventions for high-risk caregivers to improve outcomes. Following a mixed methods study to better understand these contextual factors and to address this gap between the evidence and uptake of proven strategies by caregivers, we have developed a resilience-promoting intervention to improve quality of life for family caregivers of individuals with multiple chronic conditions, including HF, Caregiver-Support. This home-based intervention is guided by effective strategies implemented by our co-investigator, [name], to support older adults in goal setting to promote healthy aging. Using these strategies, Caregiver-Support will help caregivers articulate statements of purpose in life, set goals to address fatigue and caregiver burden, provide instrumental support through a benefits check-up and promote identification and increased connection with the caregiver's social network.

The first phase of the study will be an open label pilot (N=5) followed by a single-masked, two-group, randomized trial (N=40) to test the feasibility and gauge an initial effect size of the intervention.

Participants will be visited by study staff in their homes for data collection and intervention visits.

Participants will be randomized to receive either the immediate intervention group or the waitlist control group. In the waitlist control group, participants will receive usual care for the first 16 weeks (which is limited to printed materials provided in the clinic) and then begin the intervention. The intervention will consist of 5 in-home sessions with a nurse interventionist. Each participant will receive each intervention component but interventionists will systematically tailor content to the participants' goals based on protocols. All participants will be reassessed at 16 weeks and 32 weeks by a research assistant (RA) masked to treatment condition. The primary outcome will be improvement in quality of life between baseline and 16 weeks. Other endpoints include group differences in fatigue, caregiver burden, self-reported and physiological measures of resilience up through 32 weeks after the intervention. We will also examine the acceptability of the intervention using intervention compliance and participant satisfaction data.

### 2. Objectives

Aim 1: Test the feasibility and gauge an initial effect size of the intervention to improve QOL (primary outcome), fatigue and caregiver burden (secondary outcomes) among family caregivers from baseline to 16 weeks.

Aim 2: Test whether fatigue and caregiver burden are associated with a physiological measure of resilience, inflammatory cytokines (IL-6 and IL-10) detected in sweat patches and a self-reported measure of resilience, controlling for covariates.

Aim 3: Evaluate changes in heart rate variability (HRV), an indicator of physiologic stress, pre- and post-intervention.

Aim 4: Describe care recipient 6-month palliative care utilization, all-cause hospitalization, and mortality, comparing intervention and control.

### 3. Background

Heart failure (HF) is a syndrome of multiple chronic symptoms and commonly co-occurs with 10 other chronic conditions. Nearly 30% of patients who have been hospitalized for HF will be readmitted within 30-60 days and 53% of patients hospitalized for HF will die within 5 years. As older adults manage worsening HF, caregiving responsibilities often increase, a phenomenon that has a greater impact among vulnerable populations. Throughout the provision of care, family caregivers must address a wide range of patient needs: assistance with everyday activities, help with a range of healthcare activities, transitions between settings of care, medication management and wound care. **However, because family caregivers are not routinely assessed in health care delivery, little is known about the context of their contributions to health care activities or the caregiving-related effects they experience.**

Previous studies of family caregivers of patients with HF have identified worsening quality of life (QOL) over the course of the patient's illness. For patients, being able to stay in the home as HF worsens, provides a sense of security, freedom and improved symptom awareness. However, many caregivers report increased distress while supporting the patient in the home, feeling alone and fully responsible for care. Fatigue and burden have been found to be significantly associated with decreased QOL, demonstrating the need to improve caregiver outcomes. Additionally, caregivers of patients with high symptoms perceive they spend more time on difficult tasks, have worse affective symptoms, and have poorer physical health-related QOL than those caring for patients with low symptoms. Thus, there is great need to provide interventions that improve QOL and decrease fatigue and caregiver burden of family caregivers of patients with HF, particularly in the home when patient symptoms are high.

Stress response and autonomic nervous system dysregulation have been noted among caregivers. Several cellular and systemic changes accompany the stress response network including: cytokines, namely Interleukin 6 and 10 (IL-6 and IL-10) and tumor necrosis factor alpha receptor 1 (TNF $\alpha$ R1), brain derived neurotropic factor (BDNF) and heart rate variability (HRV). Heart-rate variability detects variation in the length of time between heart beats and is considered an indirect view of autonomic nervous system function. Autonomic nervous system dysregulation is important in chronic diseases such as depression, diabetes, cardiovascular disease, stroke and certain neurological disorders. Symptoms like sleep, fatigue, and pain are also correlated with autonomic nervous system activity.

The proposed study will implement a program using evidence-based strategies. This study builds on our success in previous randomized control studies that support community dwelling, low-income, older adults with functional limitations age in place by addressing individually tailored goals to improve resilience. We will also contribute to caregiving science by evaluating implementation and maintenance of goals by participants. We will measure response to the intervention by examining both self-reported measures and physiological measures such as IL-6, IL-10 and HRV. The proposed study will address the National Academies of Sciences, Engineering, and Medicine recent call to promote the well-being of family caregivers for older adults with a focus on ensuring respect for families' diverse contexts, beliefs, and preferences.

## Innovation

The proposed study is innovative in several critical ways: 1) Supporting caregivers of patients with HF to discuss their purpose in life, set their own individualized goals, while providing instrumental and social support is both a person- and family-centered approach to improve QOL; 2) it addresses both intrinsic, individual factors and extrinsic factors through the instrumental support and social network strategies which has not been reported previously; 3) it allows participants the opportunity to tailor their goals to their own needs, rather than the heart failure management needs of the patient.

[figure not shown]
## Conceptual Framework

This study will be guided by the Society to Cells Resilience Framework (Figure 1), first-authored by [name] (co-Investigator for this pilot). The Society to Cells Resilience Framework posits that intervening on more than one socio-ecologic domain (in this case, physiologic, individual, and family) leads to more lasting effects on individual resilience compared to intervening on one domain. Second, that resilience can be fostered at critical times in the life course, such as when there are increased caregiving responsibilities that can both create meaning and strain. Based on these tenets, the resilience framework ties together the many proposed levels of measurement such as fatigue, caregiver burden and quality of life by intervening simultaneously on them to improve overall resilience.

## 4. Study Procedures

**Figure 2: Flowchart of Study Design**

control groups are used to first provide an untreated comparison and second to allow wait-listed participants an opportunity to receive the intervention at a later date. This is especially appropriate given that very few services are currently offered to HF caregivers. To account for estimated 20% attrition we will recruit 53 participants.

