### **Johns Hopkins Bayview Clinic Recruitment:**

We will distribute a recruitment flyer in the heart failure clinic at the Johns Hopkins Bayview Medical Center. Caregivers that respond to the recruitment flyer will be screened for eligibility. If they are eligible, we will contact them by phone to explain study procedures. If interested in participating, we will schedule the caregiver's baseline interview within 10 days of initial contact. During the baseline interview the research assistant will re-explain the study, obtain written consent (if interview is in-person), or e-consent (if the interview is by phone or DoxyMe or Zoom video call).

**Overview of Study Design (Figure 2):** We propose an open label pilot (n=5) with a subsequent single-blind, two group randomized pilot trial to test the feasibility and gauge an initial effect size of the Caregiver-Support intervention to improve QOL. The immediate intervention group (n=20) will receive the intervention during weeks 0-16. The waitlist control group (n=20) will be provided written materials with community resources for caregivers during the first 16 weeks, then they will begin the intervention. Waitlist

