## **Open Label Phase:**

The first five participants will be enrolled into an open label pilot study, in which they will automatically receive the Caregiver-Support intervention. The participants will be interviewed after program completion to get feedback on the data collection instruments, intervention content including the number of visits and user-friendliness of intervention components (e.g. purpose in life activity), and satisfaction with the overall program process. This feedback will be used to modify the Caregiver-Support intervention for the waitlist control trial that will begin enrollment following the open label phase.

**Randomization:** Within 48 hours of the baseline interview, we will randomize using redcap randomization and communicate the assignment to participants by letter. At that same time, we will inform the nurse interventionist of the new participant. The intervention nurse will contact the participant within one week to schedule the first appointment. The waitlisted group will receive usual care for caregivers for the first 16 weeks, which is normally limited to inclusion in some clinical assessment and teaching during patient visits. Waitlisted participants will receive monthly study postcards to encourage retention. After 16 weeks, they will begin the intervention. The 32- week assessment will measure whether immediate intervention participants continue the strategies on their own and whether they continue to improve on the self-report scales and will measure improvement following the intervention for waitlisted participants.

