## 7. Study Statistics

Exploratory and descriptive analysis will be completed for all study variables. Variables will be examined for normality and examined with means and standard deviations or medians and interquartile ranges accordingly. Baseline characteristics comparing the two groups (waitlist vs. immediate intervention) will be assessed. Any differences between the groups will be adjusted for further analysis. The significance level will be set at 0.05. Sensitivity analyses will be conducted adjusting for variables on which the group differ and compared to the pattern of results in the main analyses.

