### c. Statistical plan including sample size justification and interim data analysis.

As a pilot study, the analyses will likely not have adequate power to detect significant differences. Therefore, effect sizes, rather than statistical significance will be examined for evidence of the effectiveness of the intervention. With a total sample size of 53 we will be able to estimate the effect size associated with the intervention. This effect size will be compared to the literature for similar interventions and used to estimate the needed sample size to a fully powered effectiveness trial. There will be no interim data analysis.

Understanding the factors that predict which intervention components are successfully implemented and for which participant subgroups will be critical for fine-tuning this multicomponent intervention for future proposals that will extend efficacy examinations and effect modification analyses. Acceptability of the intervention will be examined in multiple ways. We will examine percentages of people who stayed in each arm of the study and conduct numerous descriptive correlational analyses of the association between

the intervention compliance and other variables. These analyses will quantify intervention implementation by demographic and participant health variables. Analyses that utilize the post-randomization data (e.g. treatment compliance) will be evaluated in supplementary analyses. We will distinguish non-compliance with intervention from attrition or loss to follow-up, i.e. missing data. We will also use the participant satisfaction data to examine acceptability of the intervention.

d. Early stopping rules.

As this is a low-risk behavioral intervention pilot, we have not defined any early stopping rules.

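### If the total of 53 includes the five open-label caregivers, 20% attrition leaves about 38 of 48 randomised, not the stated 40

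*Combined protocol and SAP*

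**What the plan says.** The Abstract (section 1) describes an "open label pilot (N=5) followed by a single-masked, two-group, randomized trial (N=40". The Overview of Study Design in section 4 gives the arms: "The immediate intervention group (n=20) will receive the intervention during weeks 0-16" and "The waitlist control group (n=20) will be provided written materials with community resources for caregivers during the first 16 weeks". The same overview paragraph, which the extracted text splits across two places, ends with the recruitment figure: "To account for estimated 20% attrition we will recruit 53 participants".

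The Open Label Phase paragraph of section 4 puts the first five outside the randomised comparison: "The first five participants will be enrolled into an open label pilot study, in which they will automatically receive the Caregiver-Support intervention". Enrolment to the randomised trial follows that phase.

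Section 7.c then uses the recruitment figure as the basis for estimation: "With a total sample size of 53 we will be able to estimate the effect size associated with the intervention". It makes no claim of power: "As a pilot study, the analyses will likely not have adequate power to detect significant differences".

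The text does not show how 53 was obtained. It also does not say whether 53 includes the open-label five, or whether 40 and 20 per arm are numbers randomised or numbers retained. No time point is attached to the 20%.

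**The concern.** An allowance for 20% loss is made by dividing the target by 0.8. Multiplying by 1.2 falls short, because the loss applies to the larger, inflated number. A total of 53 does not come out of the correct calculation for any target in the documents, but it does come out of the multiplication.

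Sample size is the main quantitative design input this pilot states. Section 7.c sets significance aside and relies on an effect size, which will in turn be used to size a full trial. The reader therefore needs to know how many caregivers stand behind that estimate. Section 7.c names 53, which on the most natural reading counts five people who contribute nothing to the between-group comparison. Two other uses depend on the same figures. Section 7.c looks at the percentage who stay in each arm, which needs a clear randomised denominator. The monitoring board's reports in section 8 compare expected with actual enrolment, which needs a clear expected number.

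**Working it through.** **Inputs.** Attrition 20% and recruitment total 53 (section 4, end of the design overview; 53 again in 7.c). Open-label 5, randomised trial 40 (Abstract). Arms of 20 and 20 (design overview), taken as 1:1 allocation. The open-label five are not randomised (Open Label Phase).

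**Step 1: reproduce 53.** These are the candidate derivations:

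| Calculation | Result |
|---|---|
| 40 / 0.8 | 50 |
| 40 / 0.8 + 5 | 55 |
| 45 / 0.8 | 56.25, so 57 |
| 40 × 1.2 | 48 |
| 45 × 1.2 | 54 |
| 40 × 1.2 + 5 | 53 |

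Only the last gives 53 exactly. None of the three that divide by 0.8 does.

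**Step 2: what a total of 53 implies.** If 53 is the whole study, as 7.c words it, the number randomised is 53 − 5 = 48, or 24 per arm. After 20% loss, 48 × 0.8 = 38.4 remain, about 19 per arm. To keep 40 out of 48, loss must not exceed 1 − 40/48 = 16.7%. To keep 40 under 20% loss, 40/0.8 = 50 must be randomised (25 per arm), which makes 55 with the open-label five.

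**Step 3: the alternative.** If all 53 are randomised, 53 × 0.8 = 42.4 remain and the study recruits 53 + 5 = 58. The target of 40 is then met with room to spare, since 1 − 40/53 = 24.5% could be lost. The 20% figure still does not explain 53, because 50 would have been enough.

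**Step 4: effect on precision.** The plan gives no standard deviation or interval width, so this is my own approximation. For g near zero with n per arm, the 95% half-width is about 1.96 × √(2/n):

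- n = 20: 1.96 × √0.1000 = 0.62
- n = 19: 1.96 × √0.1053 = 0.64

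For an assumed g of 0.5 and N retained in total, 1.96 × √(2/(N/2) + g²/(2N)) gives 0.64 at N = 38.4, 0.63 at N = 40 and 0.61 at N = 42.4. The readings barely differ.

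**The case against.** The strongest reply is that the derivation is a reconstruction. No text says that 40 was multiplied by 1.2, and Figure 2, which could show the split, is not reproduced in the text available. The correct figure, 55, is only two people away. This stands as far as it goes: the exact match makes 40 × 1.2 + 5 plausible, not proven. But dividing 40 by 0.8 gives a whole number, so rounding cannot turn 55 into 53.

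A reader might also infer that 53 contradicts 20 per arm. The documents do not support that. The arm sizes and the recruitment sentence belong to one paragraph, and the natural reading is that 20 per arm is the target before inflation and 53 is the inflated total. The defect is that the two are not reconciled. For the same reason, the reading that only 40 are randomised, so that 40 × 0.8 = 32 remain, ignores the recruitment sentence.

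It is also fair to say that the plan states no precision that could be undermined, and that no decision depends on reaching exactly 40. Nor does the plan place the whole 20% loss before the primary assessment at week 16. Follow-up runs to week 32, so caregivers lost after week 16 would still inform the primary comparison. The figure of 38 is therefore the number retained after 20% attrition, whenever that occurs, and not a forecast for week 16.

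**Conclusion.** The point holds in a limited form. Section 7.c calls 53 the total, and the first five are not randomised, so the best-supported reading is 48 randomised and about 38 retained, against the 40 that the inflation appears meant to protect. The allowance covers 16.7% loss, not 20%. This rests on 53 including the open-label five and on equal allocation. If all 53 are to be randomised, there is no shortfall: about 42 remain, but recruitment totals 58 and section 7.c's total is then not the study total. On either reading, a 20% allowance on the stated targets does not yield 53.

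The size is small: about two caregivers, and a half-width of g of 0.64 instead of 0.62. A reader might conclude that the pilot cannot estimate its effect size or that its arm sizes are impossible. Neither follows. What needs correcting is the stated figure and its use in 7.c as the base for a randomised comparison.

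**What to change.** Without enrolling more people:

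- In the Abstract, the section 4 design overview (including its recruitment sentence) and section 7.c, give three numbers separately: open-label, randomised, and expected retained. If 53 includes the open-label five, these are 5, 48 (24 per arm), and about 38 (19 per arm) after 20% attrition.
- Label 40 and 20 per arm as either randomised or retained. The sponsor must settle which is meant; the numbers should not be changed to 48 and 24 on inference alone.
- In section 7.c, base effect-size estimation on the randomised participants, not on 53.
- State the time point to which the 20% applies.

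If 40 retained is a firm target, the consistent figure is 50 randomised plus 5, a total of 55, which is two more than stated.

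The first route costs wording only. Its downside is that the stated number retained becomes about 38 instead of 40.

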### **Johns Hopkins Clinic Recruitment:**

Method 1: We will enroll caregivers of patients with HF treated in the Johns Hopkins Health System. Once we find potentially interested participants through clinic referral, we will screen the caregiver for eligibility then contact them by phone, zoom, or in person in clinic to explain study procedures. If eligible by screening and interested in participating, we will schedule the caregiver's baseline interview within 10 days of initial contact. During the baseline interview the research assistant will re-explain the study, obtain written consent (if interview is in-person), or e-consent (if the interview is by phone or DoxyMe or Zoom video call).

Method 2: We will distribute a recruitment flyer in adult medical/surgical clinics in the Johns Hopkins Health System. Caregivers that respond to the recruitment flyer will be screened for eligibility. If they are eligible, we will contact them by phone to explain study procedures. If interested in participating, we will schedule the caregiver's baseline interview within 10 days of initial contact. During the baseline interview the research assistant will re-explain the study, obtain written consent (if interview is in-person), or e-consent (if the interview is by phone or DoxyMe or Zoom video call).

Method 3: Caregivers of patients with heart failure will be identified through recruitment screening of [name] [name]'s study "Palliative Care Needs of Community-Dwelling Patients with Heart Failure and Physical Frailty" (IRB00262188). Patients will be sent a recruitment flyer for their caregiver. Caregivers that respond to the recruitment flyer will be screened for eligibility. If they are eligible, we will contact them by phone to explain study procedures. If interested in participating, we will schedule the caregiver's baseline interview within 10 days of initial contact. During the baseline interview the research assistant will re-explain the study, obtain written consent (if interview is in-person), or e-consent (if the interview is by phone or DoxyMe or Zoom video call).

